#### 8.2.5 ADVERSE EVENT REPORTING

For this study, only related adverse events will be reported. Adverse events will be reported to U-M IRBMED using the standard IRBMED reporting schedule: (<https://az.research.umich.edu/medschool/guidance/adverse-event-reporting>). The U-M IRBMED reporting schedule is dependent on the severity of the event, and whether such adverse events were expected. Any serious adverse events will be reported to U-M IRBMED as soon as possible but not later than 7 days of learning of the event. Non-threatening potentially serious adverse events that are causally related to the research will be reported within 14 days of learning of the event to the U-M IRBMED.

Staff will report study-related adverse events using the adverse event form in the REDCap study database promptly. In the case of a serious adverse event, the project PI and project manager should be notified by email or phone as soon as possible. Adverse events will be discussed at investigator and project staff meetings.

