## 8.2 ADVERSE EVENTS AND SERIOUS ADVERSE EVENTS

### 8.2.1 DEFINITION OF ADVERSE EVENTS

The U-M IRBMED definition of an adverse event will be used for this study. The definition can be found at <https://az.research.umich.edu/medschool/glossary> and is below:

An adverse event (AE) is any experience or abnormal finding that has taken place during the course of a research project and was harmful to the subject participating in the research, or increased the risks of harm from the research, or had an unfavorable impact on the risk/benefit ratio. The event may or may not be caused by an intervention. Adverse events also include psychological, social, emotional or financial harms.

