### 8.2.2 DEFINITION OF SERIOUS ADVERSE EVENTS

The U-M IRBMED definition of a serious adverse event (SAE) will be used for this study. The definition can be found at <https://az.research.umich.edu/medschool/glossary> and is below:

A serious adverse event (SAE) is any adverse experience occurring at any dose or level of participation that results in any of the following outcomes:

- Results in death,
- Is life-threatening,
- Requires inpatient hospitalization or prolongation of existing hospitalization,
- Results in persistent or significant disability/incapacity, or
- Is a congenital anomaly/birth defect.

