#### 8.2.4 TIME PERIOD AND FREQUENCY FOR EVENT ASSESSMENT AND FOLLOW-UP

The occurrence of an AE or SAE may come to the attention of the study team via spontaneous report or formal assessment during month 3 of the 3-month home monitoring period, where participants will be asked to describe any physical or mental health worries/concerns since they began participating in the study. Regardless of the reporting mechanism, the study team will probe any concerns to get additional information and determine if it is an adverse event. Details will be documented in the participant study record.

Any side effects that are determined to be adverse events related to study participation will be documented on the study adverse event form in the study REDCap database and followed until resolution.

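### Section 8.2.5 gives two conflicting rules for IRB reporting of a serious adverse event judged unrelated, and the REDCap adverse event form takes only events judged related

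*Combined protocol and SAP*

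**What the plan says.** **Definitions.** Section 8.2.1 defines an adverse event without regard to cause: "The event may or may not be caused by an intervention". Section 8.2.2 defines a serious adverse event by its consequences; it "is any adverse experience occurring at any dose or level of participation that results in any of the following outcomes", and none of the listed outcomes depends on causality.

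**Assessment.** Section 8.2.3.1 has all adverse events assessed by a principal investigator or, if needed, a co-investigator, and gives the severity grades. Section 8.2.3.2 has all of them placed in a related or not-related category by a trained investigator, using timing and clinical judgement.

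**Recording.** Section 8.2.4 says that the team probes every concern raised, and then: "Details will be documented in the participant study record". That sentence carries no relatedness condition. The next paragraph is narrower: "Any side effects that are determined to be adverse events related to study participation will be documented on the study adverse event form", and it attaches follow-up to resolution to those same events. Section 8.2.5 likewise has staff use the REDCap form for study-related events.

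**Reporting.** Section 8.2.5 begins "For this study, only related adverse events will be reported". It goes on: "Any serious adverse events will be reported to U-M IRBMED as soon as possible but not later than 7 days". The sentence after that reads: "Non-threatening potentially serious adverse events that are causally related to the research will be reported within 14 days". The section also asks that the PI and project manager be told promptly of a serious event, again without a relatedness condition.

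**The concern.** Two separate problems follow.

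The first is a contradiction about what goes to the IRB. The serious category includes death, life-threatening events and hospitalization. A coordinator who learns of a hospitalization judged unrelated finds one sentence that says not to report it and another that sets a 7-day limit. Two staff members could each follow the text and act differently.

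The second concerns the data. The protocol asks for a severity grade and a relatedness category for every event, but the only structured form it names is directed at one of the two categories. A not-related classification has to be made but has no specified form to hold it. An adverse event table produced from the form would show only events that passed a clinical judgement. One not-related criterion in section 8.2.3.2 is that the event is readily explained by the population's characteristics. The synopsis describes care partners as prone to depression, insomnia and stress-related disorders, while section 6.1 aims the messages at mood, sleep and activity. A worsening in those areas is therefore a kind of event on which the relatedness call is difficult, and on which the filter could matter.

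**Working it through.** No sample size, power or event rate enters this point, so there is nothing to compute. The check sets the rules side by side for the four combinations of seriousness and relatedness.

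| Event | Opening sentence of 8.2.5 | Later sentences of 8.2.5 | REDCap form (8.2.4, 8.2.5) | Participant study record (8.2.4) |
|---|---|---|---|---|
| (a) Serious, related | Report | Report within 7 days | Yes | Yes |
| (b) Non-serious, related | Report | Report on the IRB schedule | Yes | Yes |
| (c) Non-serious, unrelated | Do not report | No sentence requires it | No | Yes |
| (d) Serious, unrelated | Do not report | Report within 7 days | No | Yes |

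**Reporting conflict.** The rules agree in (a), (b) and (c) and clash only in (d). Three features of the text bear on whether (d) is a true clash:

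1. The 7-day sentence speaks of any serious event and attaches no causality condition.
2. The 14-day sentence directly after it does attach one. The condition was written where it was wanted in one sentence and is absent from its neighbour.
3. The definitions in 8.2.1 and 8.2.2 do not bring causality in by another route.

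Section 10.1.4 does not settle it, since it refers back to the study's reporting plan.

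**Form gap.** Rows (c) and (d) are off the form, although sections 8.2.3.1 and 8.2.3.2 require both to be assessed and classified. They remain in the participant study record, so they are missing from the structured adverse event data, not from every record.

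**Masking.** The documents describe no masking of anyone. Section 4.1 has the staff member who took consent assign the arm from the list. Section 8.2.3.2 gives the relatedness call to an investigator, and some of its criteria, such as whether the event eases when the intervention stops, refer to the intervention. The text does not say whether that investigator knows the allocation.

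**The case against.** **The opening sentence of 8.2.5 may set the scope.** On that reading, any serious event means any serious event among the related ones, and the timing defers to an IRB schedule that is not reproduced in the protocol. This is possible, but the section does not say so, and the explicit causal condition in the neighbouring sentence points the other way. The ambiguity stands.

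**A serious event would still reach the PI.** This is correct. The notification sentence has no relatedness condition, so the conflict concerns the onward report to the IRB and not whether the study leadership learns of the event.

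**A reader might infer that unrelated events vanish altogether.** They do not. Section 8.2.4 puts details in the participant study record and section 8.2.3 has them classified.

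**A reader might infer that relatedness is judged unblinded, or that control participants can have no related events.** The first is plausible, since the arms differ visibly, but it is not stated; only the absence of described masking is. The second is wrong. Section 8.2.3.2 covers research procedures as well as the intervention, and the risks in section 2.3.1 from the surveys and the Fitbit apply to both arms.

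**A reader might infer that worsening mood in one arm would go unseen.** The documents contradict this. Strain, anxiety and depression are rated daily in both arms and by short form at baseline and days 30, 60 and 90, and section 9.3 plans to compare the arms on all HRQOL measures. Those scores do not replace event data, but they do not depend on a relatedness call.

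**No planned analysis uses adverse events.** This is also correct. They are not an endpoint in section 3, and section 9 plans no adverse event comparison. It limits the importance of the form gap without removing it.

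**Conclusion.** The point holds in two parts. First, section 8.2.5 contradicts itself on IRB reporting of serious events judged unrelated. That is one of the four event types, and it is a conflict between stated rules, not missing detail. Second, the adverse event form leaves out both unrelated event types even though the protocol already requires them to be graded and classified. Any table drawn from the form would be filtered by a judgement with no described masking.

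The gap applies to all 60-90 participants. The number of events cannot be estimated, because the documents give no expected rates. The reporting conclusion rests on reading the 7-day sentence as written, without an implied relatedness condition. The form conclusion assumes that an adverse event summary would be built from the REDCap form, the only structured event form that the protocol names. No primary or secondary endpoint is affected. The stronger claims, that unrelated events are lost from all records or that the assessor is known to be unmasked, are not supported.

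**What to change.** 1. Reconcile the sentences in section 8.2.5 so that it is explicit whether the 7-day IRB report covers all serious adverse events or only related ones.
2. Amend sections 8.2.4 and 8.2.5 so that all adverse events and serious adverse events are entered on the existing REDCap form, with the relatedness and severity classifications that section 8.2.3 already requires.
3. Add one sentence to section 9 providing for a descriptive tabulation of all events by arm, split by relatedness, severity and seriousness.
4. State in section 8.2.4 whether follow-up to resolution still applies only to related events. Without this, putting unrelated events on the form could extend that follow-up to them unintentionally.

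The cost is a wording amendment and some extra form entries over roughly 100 days per participant. The severity and relatedness assessments are already required.

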## 9 STATISTICAL CONSIDERATIONS

### 9.1 STATISTICAL HYPOTHESES

#### Primary Endpoint:

- 1) We hypothesize that this intensive data collection protocol will be both feasible and acceptable for care partners (regardless of group assignment)
  - a. Feasibility and Acceptability as measured by  $\geq 80\%$  of participants indicating that care partners either 'Agree' or 'Totally Agree' that the different study elements are feasible and acceptable

#### Secondary Endpoints:

- 2) We hypothesize that this intensive data collection protocol will be both feasible and acceptable for care partners (regardless of group assignment)
  - a. Attrition as measured by the percent of participants completing the study (i.e., we expect  $\geq 80\%$  of participants to complete the study)
  - b. Percent missing data of total expected data for each person and on average will also be calculated to characterize the feasibility of this data collection method (i.e., we expect  $\leq 60\%$  missing data for the daily assessment questions and  $\geq 80\%$  completion rates for the three monthly surveys)

#### Exploratory Endpoints:

- 1) We hypothesize decreases from baseline to 3-months in caregiver strain among participants in the JITAI group.
- 2) We hypothesize decreases from baseline to 3-months in depression among participants in the JITAI group.
- 3) We hypothesize decreases from baseline to 3-months in anxiety among participants in the JITAI group.

## 9.2 SAMPLE SIZE DETERMINATION

The main purpose of the current trial is to establish the feasibility and acceptability of an intensive data collection protocol in order to inform the a larger, later-stage effectiveness study on the JITAI in care partners of persons with chronic medical conditions. Thus, the current study is designed to provide a point of estimate for the effect of the JITAI for this future large-scale trial. Given that there are no formal power analysis calculations for this type of analysis, we have based the proposed sample size on our previous experience conducting these types of trials. Specifically, we believe that ~50 participants will provide sufficient numbers and diagnostic diversity to evaluate feasibility and acceptability of new mobile health apps. Thus, or sample size of N=60 caregivers (30 per arm and 20 per care partner group), exceeds this estimate and should provide a reasonable range of scores on the HRQOL outcome measures to guide later phase trial work.

## 9.3 POPULATIONS FOR ANALYSES

The primary endpoint will examine survey responses on the feasibility and acceptability questionnaire that is designed to evaluate our intensive data collection protocol in the full sample (i.e., N=60 care partners). Secondary endpoints will include attrition and adherence estimates (again across the full sample). Exploratory analyses will be conducted to identify trends for an improvement in HRQOL scores (i.e., strain, depression, and anxiety) for care partners that are randomized to the intervention group. These analyses will also look for a trend for an improvement in the remaining HRQOL scores for care partners that are randomized to the intervention group, and will compare the JITAI group with the control group on all of the different HRQOL measures. Exploratory analyses may also compare important subgroups (e.g., caregiver groups that differ by diagnosis [SCI, HD or HCT], relationship type [parent vs. spousal caregivers], caregiver groups that differ by sex [male vs. female caregivers], caregiver groups that differ according to the functional status of the person with TBI (e.g., complicated mild vs. moderate vs. severe TBI or perceived functional status based on Mayo Portland Adaptability Index scores). Exploratory analyses will be an intention-to-treat approach where the participant will contribute data to the arm he/she was randomized to regardless of the amount of data contributed (i.e. the duration of participation).

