## 7 STUDY INTERVENTION/EXPERIMENTAL MANIPULATION DISCONTINUATION AND PARTICIPANT DISCONTINUATION/WITHDRAWAL

### 7.1 PARTICIPANT DISCONTINUATION/WITHDRAWAL FROM THE STUDY

Participants are free to withdraw from participation in the study at any time upon request.

An investigator may discontinue a participant from the study for the following reasons:

- Lost-to-follow up; unable to contact participant (see **Section 7.2, Lost to Follow-Up**)
- Any event or medical condition/situation that occurs that would indicate that continued collection of follow-up study data would not be in the best interest of the participant or might require treatment that would confound the interpretation of the study
- The participant meets an exclusion criterion (either newly developed or not previously recognized) that precludes further study participation
- The participant is non-compliant with the study protocol

The reason for participant discontinuation or withdrawal from the study will be recorded. Participants who provide informed consent and are randomized but do not complete the 10-day run-in period will be replaced. Participants who withdraw or are discontinued before the end of the 3-month (~90 day) home monitoring period will be replaced.

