### **8.1.5.3 MONTHLY ASSESSMENTS**

Participants will be prompted by the CareQOL app to complete a series of self-report surveys at the end of each month (day 30, 60, 90) during the 3-month (90 day) home monitoring period. They will also complete a post-intervention/app feasibility survey and retake the CAS (described above) at the end of month 3 (day 90). These surveys will be answered directly on the CareQOL app and/or by interview, and should take ~10-20 minutes to complete.

- Feasibility & Acceptability Questionnaire: At the 3-month (90 day) assessment only, participants will complete a Study Feasibility survey to assess the experience of the participant with the study methodology and technology, including the CareQOL app, Fitbit®, and the JITAI. Items are scaled from 1 to 5 to indicate level of agreement, where "1" indicates "strong disagreement" and "5" indicates "strong agreement." Administration time is 5 minutes.

Additionally, participants will update their medical history, medications, therapies, and COVID history and be queried about AEs at the end of month 3 (day 90).

- Medical History, Medications, Treatments, COVID Questionnaire. Participants will update their medical history and current treatments/management strategies (medication and non-medication – e.g., exercise, mindfulness) and COVID history. Administration time for this assessment is 10 minutes.
- Adverse Events. Participants will be asked about any changes in mental or physical health. Administration time is 5 minutes.

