#### 9.4.2 ANALYSIS OF THE PRIMARY ENDPOINT(S)

##### Primary Endpoint:

- Feasibility & Acceptability Questionnaire: At the 3-month (90 day) assessment only, participants will complete a Study Feasibility survey to assess the experience of the participant with the study methodology and technology, including the CareQOL app, Fitbit®, and the JITAI. Items are scaled from 1 to 5 to indicate level of agreement, where "1" indicates "strong disagreement" and "5" indicates "strong agreement." Administration time is 5 minutes.

Frequency counts for each of the Feasibility and Acceptability items. Descriptive statistics will also be calculated.

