**Protocol Deviations:**

This protocol uses the U-M IRBMED definition of a protocol deviation (<https://az.research.umich.edu/medschool/glossary/deviation>) which defines a protocol deviation as “an incident involving non-compliance with the protocol, but one that does not have a significant effect on the subject’s rights, safety or welfare, and/or on the integrity of the data. Deviations may result from the action of the participant, researcher or staff.”

We will follow the U-M IRBMED reporting guidance for protocol deviations found here <https://az.research.umich.edu/medschool/guidance/other-reportable-information-or-occurrence-orio>.

Reportable protocol deviations will be reported and tracked in the study REDCap database and will be discussed at investigator and project staff meetings.

The following events will not be reported as protocol deviations:

- A protocol deviation will not be reported for participants who skip/do not complete study survey questions or entire surveys (like end of month assessments or post-intervention surveys).

Participants can decline to answer any survey question for any reason. We expect in an intensive, long duration protocol like this that participants may miss some assessments.

- A protocol deviation will not be reported for out-of-window assessments. Use of this data will be assessed by the study investigators for each study analysis; some analyses may need tighter compliance to the assessment window while others will not.
- A protocol deviation will not be reported for participants who miss/do not complete the EMA assessments or do not wear/miss uploading Fitbit® data during the home-monitoring period. For example, we expect that there may be instances where participants are unable to complete the EMA assessments (for example, they are somewhere where it is inconvenient for them to answer) or forget to put on or sync the Fitbit®.
- A protocol deviation will not be reported for participants who decline the participant payment. It has been our experience that some research participants do not wish to receive payment for their participation in research studies.

Reportable protocol deviations will be reviewed at the project staff and investigator meetings.

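### The primary ≥80% agreement criterion describes day-90 responders only: it can pass alongside the ≥80% completion target while agreement among all enrolled is known only to lie between about 64-65% and 84-85%.

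*Combined protocol and SAP*

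**What the plan says.** **Primary criterion.** Section 9.1 sets the target at 80% or more "of participants indicating that care partners either 'Agree' or 'Totally Agree' that the different study elements are feasible and acceptable". Section 9.3 says that the questionnaire is "designed to evaluate our intensive data collection protocol in the full sample (i.e., N=60 care partners". Section 9.4.2 gives the analysis as "Frequency counts for each of the Feasibility and Acceptability items" plus descriptive statistics. No section gives a denominator or a rule for people who do not answer.

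**Who can answer.** Section 8.1.5.3 states: "At the 3-month (90 day) assessment only, participants will complete a Study Feasibility survey to assess the experience of the participant". Under section 10.1.7, no deviation is reported for "participants who skip/do not complete study survey questions or entire surveys (like end of month assessments or post-intervention surveys".

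**Replacement.** Section 7.1 states: "Participants who provide informed consent and are randomized but do not complete the 10-day run-in period will be replaced". It then adds: "Participants who withdraw or are discontinued before the end of the 3-month (~90 day) home monitoring period will be replaced". By sections 4.1 and 8.1.2, randomization comes before baseline data collection. By 8.1.4.3, the run-in follows baseline. Run-in failures are therefore already randomized.

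**Secondary endpoints.** Section 9.1 defines "Attrition as measured by the percent of participants completing the study", with at least 80% expected. Section 9.4.3 divides final-assessment completers by baseline completers. Section 6.2 records run-in failures as screen failures, and it limits adherence percentages to participants who are not withdrawn or lost. Section 9.3 places both attrition and adherence in the full sample.

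**Sample size.** Sections 9.2 and 9.3 say 60. Sections 1.1 and 4.1 say 60-90.

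**The concern.** The trial is meant to establish whether an intensive protocol is feasible and acceptable before a larger study. People who stop because of burden or technology are direct evidence on that question. They cannot appear in a day-90-only count, and replacement refills the sample with others.

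Other rules favour the same survivors. The screen-failure label could take randomized run-in failures out of attrition. The limit in 6.2 leaves withdrawn and lost participants out of adherence. A reader of the final report could see both 80% targets met and take this to mean that about 80% of those who started found the protocol acceptable. No planned output would show how far the data support that.

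**Working it through.** **Inputs**
- Agreement threshold of 80% and completion expectation of 80%: section 9.1.
- Sample size 60: sections 9.2 and 9.3. Range 60-90: sections 1.1 and 4.1.
- Replacement of leavers and run-in failures: section 7.1.

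**The plan's own figure.** The 60 is consistent in its make-up: 2 arms × 30 = 3 conditions × 20 = 60. The range is 3 × 20 = 60 to 3 × 30 = 90. Section 9.2 bases the number on experience and not on a formula, so there is no power calculation to reproduce.

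**Formulas.** Let E be the number enrolled, R the day-90 responders, and A the smallest count with A/R ≥ 80%.
- Lower bound (no non-responder agrees) = A/E
- Upper bound (every non-responder agrees) = (A + E − R)/E
- Without rounding, the lower bound at both minimum targets is 0.80 × 0.80 = 64%.

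**Both targets just met (80% completion).** Exact (Clopper-Pearson) 95% intervals are in brackets. In the first row, replacement continues until there are 60 completers, so E = 60/0.80 = 75.

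| Case | Completion R/E | Among responders A/R | Lower bound A/E | Upper bound |
|---|---|---|---|---|
| Replacement to 60 completers | 60/75 = 80% | 48/60 = 80% (68-89%) | 48/75 = 64% (52-75%) | 63/75 = 84% (74-91%) |
| 60 enrolled, no replacement | 48/60 = 80% | 39/48 = 81% (67-91%) | 39/60 = 65% (52-77%) | 51/60 = 85% (73-93%) |
| 90 enrolled | 72/90 = 80% | 58/72 = 81% (69-89%) | 58/90 = 64% (54-74%) | 76/90 = 84% (75-91%) |

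The primary and attrition criteria pass in every row.

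**Higher completion**
- 90%: 44/54 = 81% of responders gives 44/60 = 73%, and 65/81 = 80% gives 65/90 = 72%.
- 95%: 46/57 = 81% gives 46/60 = 77%, and 69/86 = 80% gives 69/90 = 77%.

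**If the 80% were applied to everyone enrolled**, with non-response counted as not agreeing:
- At 80% completion every responder would have to agree (48/48, 60/60 or 72/72).
- At 90% completion 89% would have to agree (48/54 or 72/81).

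**Secondary endpoints, passages side by side**
- *Attrition.* Read literally, the baseline-completer denominator in 9.4.3 keeps run-in failures who completed baseline. The label in 6.2 invites their removal. Anyone randomized without baseline data is outside the figure on either reading.
- *Adherence.* Section 6.2 leaves out withdrawn and lost participants. Sections 9.3 and 9.4.3 carry no such limit.

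**The case against.** **Responders are the natural denominator.** The endpoint is defined through item responses. The full sample in 9.3 most naturally means both arms and all three conditions pooled, in contrast to the exploratory analyses by arm. This stands. It would be too strong to say that 9.3 promises a percentage over everyone enrolled. What remains is that the plan does not state the responder base or give a rule for non-response.

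**Loss is already an endpoint, and non-response is worked against.** Attrition has its own 80% expectation under the same objective. Section 8.1.5.3 allows the questionnaire by interview, and 7.2 requires contact attempts, with a certified letter if necessary. Section 7.1 records the reasons for leaving. This also stands. The loss would be visible and should be limited, but the two figures side by side still do not show what is known about agreement among those enrolled.

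**The screen-failure tension is mild.** Section 5.4 applies the label to eligibility changes found in the run-in. Inclusion criterion 6 requires participants to be able to complete all assessments, so a run-in failure may plausibly count as an eligibility change. That is fair. What remains is that these people are already randomized when the label is applied.

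**Adherence in 6.2 may be a different calculation.** That section concerns fidelity monitoring by staff, so it need not define the endpoint. This is possible, and one sentence would settle it.

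**Conclusion.** The concern holds as a point about what the primary percentage describes. As written, the criterion is a statement about day-90 responders, and several related rules lean towards those who stayed. When both targets are just met, agreement among those enrolled is bounded only by about 64-65% and 84-85%. The lower bound is 72-73% at 90% completion and about 77% at 95%, and the gap closes at full completion. These figures rest on agreement just reaching 80% among responders and on every completer answering the item.

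A reader might infer three stronger things that the documents do not support:
- *True acceptability would be about 64%.* That is only the share known to agree. Section 7.1 lists reasons for leaving other than burden, such as medical events, so some leavers may have agreed.
- *The 80% rule should be applied to all randomized participants.* At the plan's own completion minimum this would demand unanimous agreement among completers.
- *The plan drops run-in failures from attrition.* Section 9.4.3 read literally keeps those who completed baseline. The label only makes removal possible.

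**What to change.** 1. **Sections 9.1, 9.3 and 9.4.2.** State that the 80% rule applies to day-90 responders to each item, pooled over arms and conditions, and is the only pass/fail rule for the primary endpoint. Beside it, report each item over all randomized participants, keeping replaced participants and run-in failures in, as a lower and an upper bound with exact 95% intervals. Word the conclusion as applying to responders.
2. **Section 9.4.3.** State that the screen-failure label in 6.2 does not remove randomized run-in failures from attrition. Show completion over all randomized beside the baseline-completer figure, and tabulate the reasons for leaving recorded under 7.1.
3. **Adherence.** Reconcile the population in 6.2 with 9.3 and 9.4.3. For the secondary endpoint, count the expected data of withdrawn and lost participants.
4. **Sample size.** Reconcile N=60 in 9.2 and 9.3 with the 60-90 in 1.1 and 4.1, stating whether 60 means enrolled or with day-90 data. The amendment log gives over-recruitment for missing data as the reason for 60-90, which would fit the second meaning, but no section says so.

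The cost is a few sentences and some table columns, with no new data collection. The downside is that the lower bound beside the headline, and the adherence figure, will look less favourable.
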